5.4.1. Permitted Therapies

The study will enroll subjects with an initial clinical diagnosis of aGVHD requiring systemic immunosuppressive treatment. All subjects are allowed to remain on their GVHD prophylactic immunosuppressant regimens and/or their ongoing cancer maintenance therapy. The following immunosuppressant agents are permitted:

Term	Percentage
GMOs	85%
Organic	75%
Natural	72%
Artificial	45%
Organic	88%
Natural	85%
Artificial	78%
Organic	92%
Natural	88%
Artificial	75%
Organic	95%
Natural	90%
Artificial	65%
Organic	80%
Natural	78%
Artificial	55%

5.4.2. Prohibited Therapies

- [REDACTED]
- [REDACTED]
- [REDACTED]
- [REDACTED]
- [REDACTED]

If a determination is made to treat a subject with any these therapies or medications during the study, the Medical Monitor should be informed. Subjects will be asked to remain in the study and complete the remaining visits, but no additional study drug will be administered.

5.5. Treatment Compliance

The study drug will be administered open-label in Part A and in a blinded fashion in Part B at the clinic/facility by a qualified staff member. The date and start and stop times of the infusion will be recorded.

- [REDACTED]

5.7. Enrollment or Randomization and Blinding

It is the responsibility of the investigator to ensure that subjects are eligible to participate in the study prior to enrollment and continue to remain eligible throughout the study. An interactive web response system (IWRS) will be used for the study to ensure study drug inventory, accountability and appropriate cohort allocation and blinded treatment assignment. The site's unblinded Pharmacist or designee will have access to the IWRS and all treatment assignments.

5.7.1. Part A

Part A of the study is open-label. Once informed consent has been obtained, all screening procedures have been assessed, and study eligibility has been confirmed, subjects will be enrolled to receive EQ001 on Study Day 1. The study Pharmacist or designee will access the

IWRS to enroll the subject into the study, receive cohort assignment, dose level, record drug accountability, and request resupply.

5.7.2. Part B

Part B of the study will be randomized, double blinded, and placebo controlled. Subjects will be randomized in a 2:1 ratio to an optimal dose of EQ001 (as determined in Part A) or placebo.

Once informed consent has been obtained, all screening procedures have been assessed, and study eligibility has been confirmed, subjects will be randomized to receive either EQ001 or placebo on Study Day 1. The unblinded study Pharmacist or designee will access the IWRS to randomize the subject into the study, receive the blinded treatment assignment, dose level, record drug accountability, and request resupply.

Investigators, site staff, subjects, and the Sponsor and/or designee will be blinded to treatment assignment. The unblinded pharmacist or designee will be instructed not to divulge the treatment administered of any subject with the blinded site personnel, study subject, caregiver, and/or Sponsor or designee.

The blind should be broken only if knowledge of the subject's treatment allocation would facilitate specific emergency treatment. Unblinding procedures are provided in the Pharmacy Manual. The investigator must contact the Sponsor and/or designee prior to unblinding a subject's treatment assignment. In the event of an emergency when unblinding is necessary and the Sponsor and/or designee could not be contacted, the investigator should contact the Sponsor and/or designee as soon as possible after the unblinding.

[REDACTED]

[REDACTED]

[REDACTED]

[REDACTED]

[REDACTED]

Upon completion or termination of the study, all unused and partially used (if allowed by site/institutional procedure to be retained) investigational product must be returned to the Sponsor (or designated agent) unless the Sponsor authorizes the study site to destroy investigational product.

If the Sponsor authorizes the study site to destroy investigational product, the investigator is responsible to ensure that arrangements are made for proper disposal. Written authorization should be issued by the Sponsor; procedures for proper disposal should be established according to applicable regulations, guidelines, and procedures; and appropriate records of the disposal should be documented and forwarded to the Sponsor.

If the study site is unable to destroy the investigational product, the unblinded study monitor will facilitate the return of unused and/or partially used investigational product.

6. STUDY PROCEDURES

Subjects in Parts A and B will have the same study assessments except as noted. The following assessments will be conducted during screening and at selected time points specified in the Schedules of Events [REDACTED] and in Protocol [Section 8](#). Additional procedures deemed necessary as part of standard of care may be performed at the discretion of the investigator. All missed visits and any performed procedures that are not protocol-specified activities must be documented in the subject's medical record and the appropriate electronic case report form (eCRF).

6.1. Screening and Informed Consent

Before subjects commence any study-specific activities or procedures, the Sponsor requires a copy of the study site's written Institutional Review Board (IRB) approval of the protocol, informed consent form (ICF), and all other subject information and/or recruitment material, if applicable. Each subject (or legally acceptable representative) must sign and date the ICF before participating in study-specific activities.

After the ICF is signed, the subject enters screening. Each subject will be assigned a unique subject number at the time of screening. Subject numbers will be sequential within each study site. If more than one (1) assessment is performed during screening, the initial assessment closest to the enrollment date and time will be used for eligibility. Subjects must have their first dose of study drug within 72 hours (3 days) of their first corticosteroid dose, therefore, sites should consent and start screening subjects as soon as aGVHD is suspected.

This subject number, assigned at the time of screening, will be used to identify the subject throughout the study and must be used on all study documentation related to that subject. The subject identification number will remain constant throughout the entire study; it must not be changed after initial assignment. Each study site will maintain a list identifying all subjects by subject identification number and initials.

After completing the screening period, the subject will be evaluated by the investigator to confirm eligibility. A subject is considered enrolled when the investigator decides that all of the eligibility criteria are met. The investigator will document this decision and date and time in the subject's medical record and the eCRF. Screen failure subjects will be entered into the eCRF. Investigators will maintain a screening log of all potential study candidates that includes limited information about each candidate, dates, and outcome of screening process (e.g., enrolled into study, reason for ineligibility, or withdrawal of consent).

6.2. Demographics and Medical History

Demographic data including sex, age, race, and ethnicity will be collected.

The investigator or designee will collect medical and surgical history that started prior to enrollment, including information on the subject's concurrent medical conditions. All findings will be recorded on the medical history eCRF.

[REDACTED]

[REDACTED]

[REDACTED]

[REDACTED]

6.3. Physical Exam

The investigator or designee will conduct a complete physical exam during screening and a targeted physical exam at selected time points thereafter. Physical exam finding prior to the first dose of study drug will be recorded on the medical history eCRF page and clinically significant findings after the first dose of study drug will be recorded as AEs.

At a minimum, the complete physical exam should include assessments of the head and neck, skin, nervous system, lungs, cardiovascular system, abdomen, thyroid, lymph nodes, and extremities.

A targeted physical exam will include assessment of any new subject complaints or changes from baseline, including clinical grade of aGVHD at diagnosis and organ involvement at diagnosis, infusion-related reactions, and examinations for potential hypersensitivity reactions.

6.4. Vital Signs

The following vital sign measurements will be performed: systolic and diastolic blood pressure, pulse, respiration rate, and temperature. On dosing days, vital signs will be monitored pre-dose and every 30 minutes (\pm 5 minutes) [REDACTED]

[REDACTED] The subject must be in seated or in a semi-recumbent position in a rested and calm state for at least 10 minutes before vital signs are collected. The position selected for a subject should be the same throughout the study and documented on the vital signs eCRF.

Height will be measured without shoes at screening.

Weight without shoes will be obtained at screening. On dosing days, weight will be collected pre-dose. The weight at screening will be used to calculate all study drug doses unless there has been a change in weight by 20% or greater. An additional subsequent change in dosing will not occur unless there is a change in weight of 20% or more from the new weight that required the dosing change to be made (no longer referencing back to the Screening weight at subsequent doses).

[REDACTED] [REDACTED]

[REDACTED]

[REDACTED]

[REDACTED]

Cancer Type	Control (%)	T1 (%)	T2 (%)
Lung	100	100	100
Stomach	100	100	100
Colon	100	100	100
Liver	100	100	100
Pancreas	100	100	100

6.7. Biopsy Review

Any relevant tissue biopsy (eg, gastrointestinal, liver, bone marrow, or skin), performed per standard of care to support the clinical diagnosis and/or management of a subject's aGVHD at any time prior to and during the subject's enrolment, should be collected and the clinical data derived from the biopsy entered into the eCRF. Biopsies that were performed prior to and during screening to confirm the diagnosis of aGVHD should be recorded.

6.8. Minimal Residual Disease (MRD)

Assessments of MRD should be captured if they were done anytime from the time of the HSCT through baseline (Day 1).

6.9. Chronic GVHD (cGVHD)

An assessment of cGVHD will be performed during the long-term follow-up visits.

6.10. 12-Lead Electrocardiography

The subject must be in a seated, semi-recumbent, or supine position in a rested and calm state for at least 10 minutes before ECG assessment is conducted. Each 12-lead ECG should be performed prior to blood draws, dosing (if applicable, except for Baseline post-dose ECG), or other invasive procedures.

In Part A, a single ECG will be recorded using the site's standard ECG equipment. The investigator or designated study site physician will review, sign, and date all ECGs. The original ECGs will be retained with the subject's source documents. At the request of the Sponsor, a copy of the original ECG will be made available to the Sponsor. Each ECG should capture QRS, QT, QTc, RR, and PR intervals and be documented on the ECG eCRF.

In Part B, ECGs in triplicate taken over 5 minutes will be recorded using the ECG equipment provided and transmitted to a central ECG reader. The ECG results will be assessed by blinded, independent, central review to evaluate changes in ECG intervals and morphology as compared

[figure not shown]
with pretreatment ECGs. An ECG manual will be provided. The investigator or designated study site physician will also review, sign, and date all ECGs. The original ECGs will be retained with the subject's source documents.

Any clinically significant abnormal ECG findings will be recorded as AEs.

6.11. Clinical Laboratory Tests

6.11.1. Local Laboratory Parameters

Blood samples will be collected [REDACTED] [REDACTED], Protocol [Section 8](#) and below. All safety laboratory test will be conducted at the local clinic/facility. Samples will be collected pre-dose on study dosing days. Repeat laboratory testing is not required if a test was already performed within the specified time window for collection. Samples may be analyzed for the tests outlined in this protocol and for any additional tests necessary to ensure subject safety. These may include, but are not limited to, investigation of unexpected results. Subjects will be in a seated, semi-recumbent, or supine position during blood collection. [REDACTED]

6.11.2. Central Laboratory Parameters

Blood, skin biopsy, and stool samples will be collected [REDACTED] [REDACTED] Protocol Section 8 and below from screening through the follow-up visits and submitted to the central laboratories for analysis. [REDACTED]

6.11.2.1. Pharmacokinetic

In Part A only, serum will be assayed for EQ001 concentrations using a validated assay. PK samples will be collected at time points specified below. Based on emerging PK data, the actual collection times may change after discussion between the investigator and Sponsor. [REDACTED]

6.11.4. Research Use of Stored Human Samples, Specimens, or Data

De-identified data obtained from this study may be shared with other academic institutions after completion of the study. Furthermore, any remaining plasma, blood, and tissue samples may be stored for future analysis to help understand the markers for disease state, progression, and response to treatment as new discoveries emerge. [REDACTED]

[REDACTED]

[REDACTED]

[REDACTED]

6.12. Removal of Subjects from the Study

At any time, the investigator can remove a subject from the study or stop study drug dosing if deemed necessary for subject safety. The Sponsor also reserves the right to terminate the study at any time. All data normally collected at completion of the study must be collected at the time of the subject's early termination or termination of the study (see [Section 8.12](#) or [Section 8.15](#), as appropriate). If consent has not been withdrawn, AEs will continue to be collected as described in [Section 7](#).

A termination case report form (CRF) page will be completed for every subject enrolled, whether or not the subject completed the study. The reason for any early discontinuation from the study should be indicated on this form. Separate CRF entries will document whether each subject completed all doses of study drug, or if not, the reason a subject terminated study drug early.

The investigator will discuss with the subject/subject's parent(s) or legally acceptable representative(s) the most appropriate way to withdraw to ensure the subject's health. Should a subject (or a legally acceptable representative) request or decide to withdraw consent, all efforts will be made to complete and report the observations as thoroughly as possible up to the date of withdrawal.

7. ADVERSE EVENTS

An AE is any unfavorable and unintended sign (including an abnormal laboratory finding), symptom, or disease or any worsening of a pre-existing condition temporally associated with the use of a study drug, whether or not related to the study drug. AEs that occur after the first dose of EQ001 or during the study treatment and safety follow-up periods will be documented on the AE eCRF. The investigator will assess the AE severity and relationship of the AE to study drug. The investigator will treat the subject as medically required.

Laboratory values that are outside the laboratory reference range should be reported as AEs only if considered clinically significant by the investigator.

From the time of obtaining informed consent through the first administration of study drug, all SAEs and nonserious AEs related to protocol mandated procedures will be recorded on the SAE/AE eCRF. All other untoward medical occurrences observed during screening, including exacerbation or changes in medical history, will be captured on the medical history eCRF. Details on recording and reporting AEs are provided below.

AEs will be collected through Study Day 169 for subjects who complete study drug through Day 57. AEs will be collected through Study Day 85 for subjects who discontinue study drug early. Recent hospitalizations and SAEs, if applicable, will be recorded at the Day 253 and 337 visits.

The investigator's clinical judgment should be used to determine whether a subject is to be withdrawn due to an AE. In the event the subject requests to withdraw from study-related treatment, the subject should be asked to return for all remaining study visits through Study Day 169. In the event a subject is withdrawn from study, an early-termination visit should be completed.

All subjects experiencing AEs while on study drug, including clinically significant abnormal laboratory values, whether or not associated with use of the study drug, must be monitored until the condition returns to normal, returns to the subject's baseline, until the investigator determines the AE has reached a stable outcome and is no longer clinically significant, or the subject is considered lost to follow up.

If consent has not been withdrawn, all deaths should be reported through Study Day 337, even if study drug has been discontinued.

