In addition, if at any time up to Study Day 169, a subject has an unscheduled study visit, all procedures that were conducted at the visit will be collected in the electronic case report form (eCRF) as an unscheduled visit. If a subject experiences disease progression or recurrence, the subject should complete an unscheduled visit that includes disease assessments and grading.

Safety and Long-Term Follow-Up:

All subjects who complete study drug dosing will be evaluated on Study Day 169 for disease progression assessments, aGVHD organ stages and overall clinical grading, aGVHD-AI, PK [REDACTED], ADA, and AE monitoring .Collection of concomitant medications may be required after Day 85 through Day 169, if requested by the Sponsor for any ongoing safety concerns related to study drug.

During the Long-Term Follow-Up period, the site will phone subjects on Study Days 253 and 337 to collect information on disease status (disease relapse or cGVHD), long-term survival, and safety (eg, recent hospitalization or SAEs).

Dose Modification and Dose Schedule Deviation:

In Part A, if a subject has a DLT during the DLT window (Study Days 1-29), study drug dosing will be discontinued for that subject. Subjects experiencing a DLT will be encouraged to remain in the study and complete the remaining visits; the subjects will not be replaced. If a subject terminates early for a reason other than a toxicity during the DLT window, the subject may be replaced.

In the event of a clinically significant AE that is not a DLT, study drug dosing may be temporarily withheld, and supportive therapy administered, as clinically indicated. If the toxicity resolves to baseline or Grade 1 prior to the next scheduled dose, dosing may be continued at the next scheduled dosing visit as follows, with agreement of the Sponsor and/or Medical Monitor:

- at the assigned dose (subjects in Part A or Part B) or
- at the next lower dose level evaluated in Part A (subjects in Part B only)

Data and Safety Monitoring Committee (DSMC), Dose-Limiting Toxicity, and Stopping Criteria:

A DSMC will review all available clinical and laboratory safety data at defined intervals during the conduct of each cohort in Part A and periodically during Part B of the study. The DSMC will make recommendations regarding the continuation, discontinuation, or modification of the study, cohort advancement (during Part A), and progression to Part B of the study.

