Part B of the study will be randomized, double blinded, and placebo controlled, and will commence following the completion of Part A and approval by the DSMC. In Part B, approximately 60 subjects will be enrolled to better define the safety, tolerability, [REDACTED], and to explore the clinical activity of EQ001 in subjects with newly [REDACTED] [REDACTED] aGVHD.

[figure not shown]
After informed consent has been obtained, all subjects will be screened for potential participation, and those meeting eligibility criteria will be offered participation in the study. The study will enroll subjects with an initial clinical diagnosis of aGVHD requiring systemic immunosuppressive treatment. All subjects must receive their first dose of study drug within 72 hours (3 days) of the subject's initial systemically administered corticosteroid dose.

The systemically administered corticosteroid treatment will be prednisone, at approximately 1-2 mg/kg/day (or its equivalent) at the time of first dose of study drug administration; however, the investigator can adjust dosing as clinically indicated during the study according to the recommended treatment and tapering schedule [REDACTED]

Subjects in Parts A and B will have the same study assessments except as noted. All subjects will have two (2) months of dosing comprising five (5) doses of study drug, administered IV every fourteen (14) days, and ten (10) months of follow up for a total of twelve (12) months in the study. The follow-up period will consist of a 2-month Safety Follow-Up period (through Day 169) and then an 8-month Long-Term Follow-Up period (through Day 337). [REDACTED]

[REDACTED] overview of the study timeline for Part A and Part B, respectively. During the Long-Term Follow-Up period, the site will phone subjects on Study Days 253 and 337 to collect information on disease status (disease relapse or cGVHD), long-term survival, and safety (eg, recent hospitalization or SAEs).

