9.7. Safety Analysis

All safety data summaries will use the safety population.

For subjects in Part A, number and percent of subjects experiencing any DLTs will be presented by cohort. A listing of DLTs will also be provided.

AEs will be coded using the Medical Dictionary for Regulatory Activities (MedDRA) and will be graded by the investigator using the CTCAE v5.0 or the current version. Subject incidence of TEAEs, treatment-emergent serious AEs (TESAEs), TEAEs leading to treatment discontinuation and TEAEs with an outcome of death will be summarized by SOC and preferred term (PT). AEs will also be further summarized by worst severity grade and relationship to study drug. [REDACTED]

[REDACTED]

[REDACTED]

Clinical laboratory data will be summarized descriptively, these summaries will include observed values at collection timepoints and change from baseline. All laboratory parameters that can be graded using the CTCAE will be graded. [REDACTED]

[REDACTED]

[REDACTED]

[REDACTED]

[REDACTED]

[REDACTED]

[REDACTED]

[REDACTED]

[REDACTED]

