6.10.1 Adverse Events

Adverse events will be coded using the Medical Dictionary for Regulatory Activities (MedDRA) Version 20.1 or higher and graded by the investigator using the CTCAE v5.0 or the current version. All adverse events (AEs) will be classified as either pre-treatment AEs or treatment-emergent AEs (TEAEs) as follows:

- Pre-treatment AEs are events that start prior to the date of first dose of study treatment that do not qualify to be treatment-emergent as per the definition below.
- TEAEs are events with start date on or after the first dose of study treatment or events that started prior to the first dose of study treatment whose severity worsened on or after the first dose of study treatment. All adverse events considered by the investigator as at least possibly related to the study treatment will be considered as treatment-emergent irrespective of the start date.

Subject incidence of treatment-emergent TEAEs, treatment-emergent serious AEs (TESAEs), DLT AEs, TEAEs leading to treatment discontinuation and TEAEs with an outcome of death will be summarized by SOC and PT. These Adverse events will also be further summarized by worst severity grade and relationship to study treatment.

TEAEs of special interest (TEAESIs) will also be summarized by SOC, PT, and worst severity grade.

All AE data will be listed for each cohort. Treatment-emergence status will be flagged in the listing. In addition, listings of serious AEs (SAEs), AEs leading to discontinuation of study treatment and AEs resulting in death will be produced.

Statistical Analysis Plan

Sponsor Name: Equillium Inc.

Sponsor Protocol ID: EQ001-aGVHD-001

The severity of all AEs is recorded as mild, moderate, or severe. The relationship between an AE and study treatment is assessed as Not Related, Unlikely Related, Possibly, Probably, Related by the investigator. A study treatment-related AE is an AE considered by the investigator as one that is at least 'possibly related' to study treatment or with unknown/missing relationship to study treatment.

An overview table will summarize the number and percentage of subjects with at least one of the following TEAEs, where subjects with more than one TEAE in a particular category are counted only once in that category:

- Any TEAE
- Any DLT AE

- Any TEAE by severity (mild, moderate, severe)
- Any TEAE related to study treatment
- Any Grade 3 or higher TEAE
- Any TEAE leading to study treatment discontinuation

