- Any TEAE leading to discontinuation from the study
- Any TEAE with an outcome of death
- Any TESAE
- Any TESAE related to study treatment
- Any TESAE with an outcome of death
- Any TESAE related to study treatment with an outcome of death
- Any TESAE leading to treatment discontinuation
- Any TESAE leading to discontinuation from the study

The number and percentage of subjects reporting TEAEs will be summarized by SOC and PT. Tables will be sorted by the descending order of incidence in overall total column with respect to SOC first and descending order of incidence with respect to PT within SOC. The following summaries will be produced:

- TEAEs by SOC and PT
- DLT AEs by SOC and PT
- TEAEs related to study treatment by SOC and PT
- TEAEs by worst severity grade by SOC and PT
- TEAEs leading to the discontinuation of study treatment by SOC and PT
- TESAEs by SOC and PT
- TESAEs related to study treatment by SOC and PT
- TEAEs with an outcome of death by SOC and PT

Statistical Analysis Plan

Sponsor Name: Equillium Inc.

Sponsor Protocol ID: EQ001-aGVHD-001

- TESAEs with an outcome of death by SOC and PT

In the above summaries, subjects with more than one AE within a particular SOC are counted only once for that SOC. Similarly, subjects with more than one AE within a particular PT are counted only once for that PT. For summaries by worst severity grade, subjects with multiple AEs within a particular SOC or PT will be counted under the worst severity grade within that SOC or PT.

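### AEs are collected to Day 169 for completers but only to Day 85 for early stoppers, and no common window is planned: Part B TEAE incidence can be distorted, in an unknown direction

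*Protocol*

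**What the plan says.** **Collection.** Protocol Section 7 sets two windows. For completers: "AEs will be collected through Study Day 169 for subjects who complete study drug through Day 57". For the rest: "AEs will be collected through Study Day 85 for subjects who discontinue study drug early". The Protocol synopsis (Safety and Long-Term Follow-Up) follows the same split for the visit that includes AE monitoring: "All subjects who complete study drug dosing will be evaluated on Study Day 169".

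**Other statements that bear on the window.** The opening paragraph of Section 7 says that AEs arising in the treatment and safety follow-up periods are documented, and Section 3.1 runs safety follow-up through Day 169. For a subject who asks to stop treatment, Section 7 adds that "the subject should be asked to return for all remaining study visits through Study Day 169". The synopsis (for subjects with a DLT, and for dosed subjects generally) and Section 5.4.2 (after a prohibited therapy) also ask or encourage subjects to keep attending.

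**Analysis.** SAP 6.10.1 defines the events by their start only ("TEAEs are events with start date on or after the first dose of study treatment", plus events that worsen after the first dose or are judged related) and gives no end date. It reports counts and percentages: "The number and percentage of subjects reporting TEAEs will be summarized by SOC and PT". Protocol 9.7, which covers both parts, plans the same measure: "Subject incidence of TEAEs, treatment-emergent serious AEs (TESAEs), TEAEs leading to treatment discontinuation and TEAEs with an outcome of death will be summarized". The denominator is everyone who received any study drug (Protocol 9.3.1, SAP 4.1). SAP 6.6 describes exposure only as number of doses. Within safety, the visible SAP uses Kaplan-Meier only for selected laboratory grade increases (6.10.2).

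**The concern.** A crude percentage assumes that everyone in the denominator was watched for the same time. Here the time depends on something that happens after treatment starts, namely whether the subject finished dosing. If one group has more early stoppers, less of its observation time falls in Days 86-169, and a difference in TEAE percentages can appear with no difference in risk.

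The subjects with the shorter window include those of most safety interest. A Part A subject with a DLT stops dosing, and so does a Part B subject with uncontrolled drug-related toxicity (Protocol 3.2.2). Safety is a primary objective of Part A and a secondary objective of Part B. Non-serious events that were never recorded cannot be recovered at analysis.

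**Working it through.** The documents state no TEAE rate, discontinuation rate or power figure on this point, so there is no planned number to reproduce. The check is day arithmetic on the stated windows, followed by a simple model with assumed inputs.

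**1. Windows.** The schedule is "five (5) doses of study drug, administered IV every fourteen (14) days", so doses fall on Days 1, 15, 29, 43 and 57.

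- Completers: 169 − 1 = 168 days of AE collection from first dose.
- Early stoppers: 85 − 1 = 84 days, exactly half.

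**2. General size.** Let d1 and d2 be the early-stopping proportions in two groups with the same true risk, and q the probability of a first event in Days 86-169, taken to be the same for stoppers and completers. Each early stopper loses those late first events from the count, so:

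spurious difference (group 2 − group 1) = −(d2 − d1) × q

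**3. Constant hazard.** Let p be the true incidence by Day 169 and s = √(1 − p) the chance of being event-free at Day 85. Then q = s − s², and the observed incidence in a group is (1 − d)p + d(1 − s). The quantity s − s² is largest at s = 0.5, that is p = 75%, where it equals 0.25. Under this model the distortion therefore cannot exceed one quarter of the difference in stopping rates.

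**4. Illustration with assumed stopping rates of 20% and 40%:**

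| True incidence p | s | q = s − s² | Observed, 20% stop | Observed, 40% stop | Difference (points) |
|---|---|---|---|---|---|
| 10% | 0.949 | 4.9% | 9.0% | 8.1% | −1.0 |
| 25% | 0.866 | 11.6% | 22.7% | 20.4% | −2.3 |
| 50% | 0.707 | 20.7% | 45.9% | 41.7% | −4.1 |
| 75% | 0.500 | 25.0% | 70.0% | 65.0% | −5.0 |
| 99% | 0.100 | 9.0% | 97.2% | 95.4% | −1.8 |

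Worked row, p = 75%: 0.8 × 0.75 + 0.2 × 0.50 = 70.0%; 0.6 × 0.75 + 0.4 × 0.50 = 65.0%. With 20% v 50% stopping, the maximum is 0.30 × 0.25 = 7.5 points. The constant-hazard ceiling does not apply to events that occur only late: if 30% of subjects would have such an event, 20% v 40% stopping gives 0.20 × 0.30 = 6.0 points.

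**5. Against sampling error.** In Part B with 40 v 20 subjects and p = 0.5, the standard error of a difference is √(0.25/40 + 0.25/20) = 13.7 points. In a Part A cohort of 6, 5 points is 0.05 × 6 = 0.3 of a subject.

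**6. Does the fix work?** With equal hazards, a window common to all through Day 85 gives 1 − s in both arms whatever the stopping rates: 13.4% in both at p = 25%, and 50.0% in both at p = 75%. First events per time at risk also agree at 20% and 40% stopping: 0.171 per 100 subject-days at p = 25%, and 0.825 at p = 75%.

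**The case against.** **A reader might infer that the group tolerating treatment worse will look safer.** The documents do not support that. Dosing also stops because the subject is judged unlikely to benefit, withdraws consent or cannot comply (Protocol 3.2.2), or receives a prohibited therapy (5.4.2). If more placebo subjects stop for lack of benefit, placebo gets the shorter window and EQ001 looks worse. Nor need the observed rate be lower in the group with more stoppers. Under the constant-hazard model, a hazard in early stoppers twice that of completers offsets the halved window (168/84 = 2). A subject who stops because of a TEAE is also already counted in the any-TEAE row.

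**A reader might infer that Part A's safety conclusions or escalation decisions are compromised.** Escalation rests on DLTs in Days 1-29, well before Day 85, and cohorts of 3 to 6 are only described.

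**A reader might infer that all safety data stop at Day 85.** Section 7 has deaths reported through Day 337 even after drug is stopped, and hospitalizations and serious AEs recorded at Days 253 and 337. Section 7.4 requires every serious AE to be reported whatever its cause. The protection for serious AEs is partial, because Section 7 limits the later contacts to recent events without saying how far back that reaches.

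**A reader might infer that early stoppers' later visits certainly take place.** Attendance is requested or encouraged, not assured, and the detailed visit schedule is redacted.

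**Visibility.** The visible SAP addresses Part A, and text is redacted after the AE paragraph of Protocol 9.7 and missing elsewhere in the SAP. A further rule could exist there.

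All of this narrows the point. What stands is that the collection windows differ, the visible TEAE summaries do not allow for it, and Section 7 is at odds with itself.

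**Conclusion.** The concern holds in a limited form. As written, TEAE percentages combine 168-day and 84-day observation according to whether dosing was completed. If stopping rates differ, incidence of AEs with first onset in Days 86-169, mainly non-serious, is understated relative to full collection in the group with more stoppers. This assumes similar late-event rates between groups and between stoppers and completers.

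The size cannot be fixed from the documents. The 1 to 5 points at 20% v 40% rest on assumed stopping rates and a constant hazard. The effect is small for rare events and for near-universal rows, and largest for moderately common or late-onset events. It matters mainly for the Part B comparison. There it is smaller than the standard error, but it is systematic: it does not average out, and it cannot be repaired later for events not collected.

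Independently of any bias, Section 7 needs reconciling. Its opening paragraph, read with Section 3.1, covers AEs through Day 169, while the later sentence ends collection at Day 85 for early stoppers. Sites could apply either.

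**What to change.** 1. **Protocol Section 7.** Reconcile the passages so that AEs are collected through Day 169 for every dosed subject who has not withdrawn consent, whether or not dosing was completed, using the visits these subjects are already asked to attend. Align the synopsis text on the Day 169 evaluation.
2. **Part B analysis.** Base between-arm TEAE tables on a window common to all subjects, stated in advance. If Section 7 is left unchanged, that window should end at Day 85, with later events shown separately.
3. **Optional supplement.** Add exposure-adjusted incidence rates. These also allow for subjects who leave the study before the common cut-off, though a single rate summarises well only if the hazard is roughly constant.

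The cost is a little more data entry and one extra set of tables. No dose, treatment or visit changes. A Day 85 window alone makes the comparison fair but leaves out later events, so step 1 is the better remedy where it is still possible.
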